## 9. STATISTICAL CONSIDERATIONS

#### 9.1 Sample Size and Power Analysis

The study is designed to test the null hypothesis that the treatment group and control group are not different (see 2.3). Specific reference is made to the number of subjects who achieve a  $\geq$ 50% reduction in stress urinary incontinence episodes per day when comparing the final outcome to a baseline measure. Several comparable studies were identified in the literature in which similar " $\geq$ 50% reduction in episodes" metrics were reported. From these, sample-size calculations were performed to provide confidence that sufficient subjects would be enrolled to protect against Type II error. Each of these calculations target 80% power and assume an alpha of 2.5%, a 2:1 treatment to control randomization ratio, and a single-tailed test.

• From Sand *et al*, 48% of subjects in the active group (2 treatments per day) were responders compared to 13% of subjects in a control (sham) group. Using these values in a chi-squared sample size calculation one finds that the treatment group for the proposed study needs to enroll 31 subjects.

<sup>1 Sand et al, "Pelvic floor electrical stimulation in the treatment of genuine stress incontinence: A multi-center, placebocontrolled trial", Am J Obstet Cycecol, 173(1):72-79, July 1995.

- From Richardson *et al*, 62% and 73% of subjects (1 treatment/day and 1 treatment every other day) were responders. This study makes reference to the response rate for the sham group in the Sand et al study (13%). Using the 62% and 13% values in a chi-squared sample size calculation one finds that the treatment group for the proposed study should include 16 subjects.
- From a similar, ongoing study in which Elidah is also the Investigator (WIRB-20162650), to date, 71% of subjects are responders. Conservatively estimating the control responder rate at 15% (about the average rate reported in the AHRQ meta-analysis for the control groups in studies using vaginal EMS, Table F97), using a chi-squared sample size calculation one finds that the treatment group for the proposed study needs to enroll 12 subjects.

These three analyses suggest a treatment group in the range of 12-31 subjects. Taking a conservative approach, Elidah will aim to enroll 40 subjects in the treatment group and 20 subjects in the control group. At that level of enrollment, responder rates of 60% and 25% would give p=0.01. Anticipating that some subjects will drop out throughout the study, a total of 70-80 subjects will be identified for participation. See 9.4 regarding interim analysis and stopping rules.

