### 5.2 Number of Subjects

An analysis of statistical power determined that 40 subjects in the active group and 20 subjects in the control group is likely sufficient to achieve statistical significance with respect to the primary outcome measure. Appreciating that some subjects who are initially enrolled will fail to complete treatment and return the study materials, it is likely that 70-80 subjects will be enrolled. See 9.1 for discussion of the sample size calculation.

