### 9.5 Data Analyses

Analysis of the **primary efficacy endpoint** will proceed as follows. Each adherent subject's Daily Log will be used to determine the average number of SUI episodes per day for the baseline and  $12^{th}$  weeks (see 5.5 regarding subject adherence). To accommodate the likelihood that some subjects will omit log data, the "weeks" referred to in the baseline and 12th week assessments refer to the first and last 5 entries in the Daily Log. The percent reduction in SUI episodes is then calculated by subtracting the final week average from the baseline average, dividing the difference by the baseline average, and multiplying by 100. Subjects with a percent reduction of  $\geq$ 50% are considered responders. The number of responders from each group is then compared using a one-tailed Fisher's exact test for groups of unequal size, and p $\leq$ 0.025. For example, if 24 of 40 subjects (60%) from the active group responded and 5 of 20 (25%) from the control group responded, the active treatment would be considered effective (p=0.01).

SUI episodes per day data can additionally be characterized simply in terms of percent reduction (independent of whether it reaches a 50% level of clinical significance) and the treatment groups analyzed using a 2 sample t-test with unequal group sizes. This approach is commonly reported in the literature. This value may additionally be reported but is not intended for use in determining whether the study met its endpoint. This use of a secondary analysis method on a single endpoint after success of the primary analysis method is generally understood to not inflate the Type 1 error rate, so no multiplicity adjustments are necessary.

Also note that confidence intervals and associated effect size calculations may also be made on the same data, but no multiplicity adjustments are warranted. Similarly, the data may be additionally analyzed using intent-to-treat criteria instead of with per-protocol criteria as defined in 5.5.

Regarding **secondary outcome measures**, three tests are prospectively defined with the intent of using the results to support future product labeling and marketing. The Hochberg procedure

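### Section 9.1 sizes the trial with a chi-squared formula, but 9.5 decides it with Fisher's exact test; 80% power then needs 22-46 in the treatment group, not 12-31, so 40 is not conservative

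*Combined protocol and SAP*

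**What the plan says.** Section 9.1 sets common assumptions for its three calculations: "Each of these calculations target 80% power and assume an alpha of 2.5%, a 2:1 treatment to control randomization ratio, and a single-tailed test". The scenarios are 48% v 13% (a published sham-controlled trial), 62% v 13% (a second published study, with the sham rate borrowed from the first) and 71% v 15% (the sponsor's own ongoing study, with an assumed control rate). For the first it reports: "Using these values in a chi-squared sample size calculation one finds that the treatment group for the proposed study needs to enroll 31 subjects". The other two give 16 and 12. It then concludes: "These three analyses suggest a treatment group in the range of 12-31 subjects", and goes on: "Taking a conservative approach, Elidah will aim to enroll 40 subjects in the treatment group and 20 subjects in the control group". On losses it adds: "Anticipating that some subjects will drop out throughout the study, a total of 70-80 subjects will be identified for participation". Section 5.2 tells the reader that "40 subjects in the active group and 20 subjects in the control group is likely sufficient to achieve statistical significance".

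Section 9.5 specifies a different test for the primary endpoint: "The number of responders from each group is then compared using a one-tailed Fisher's exact test for groups of unequal size", with success at p≤0.025. It also restricts who is counted: "Each adherent subject's Daily Log will be used to determine the average number of SUI episodes per day". Neither section gives a sample size or a power for Fisher's test.

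**The concern.** A sample size describes the test that it was computed for. Fisher's exact test is conservative in small samples. A size that gives 80% power under a large-sample formula will usually give less under Fisher, and with 20 controls the gap can matter. Anyone reading 9.1 and 5.2 would conclude that 40/20 sits comfortably above the most demanding of three requirements. If that is not so for the test that decides the trial, the protection against a false negative is overstated, and nothing in the documents reveals it.

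**Working it through.** **Inputs.** From 9.1: one-sided alpha 0.025 (z = 1.96), power 80% (z = 0.8416), 2:1 allocation, and the three pairs of rates. From 9.5: one-tailed Fisher's exact test, p≤0.025. Below, p1 and p2 are the active and control rates, q = 1 − p, d = p1 − p2, and n1 is the treatment-group size.

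**Step 1: reproduce the plan's figures.** The unpooled formula is n1 = (1.96 + 0.8416)² × [p1q1 + 2p2q2] / d², and (1.96 + 0.8416)² = 7.849.

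- 48% v 13%: 7.849 × (0.2496 + 0.2262) / 0.1225 = 30.49, so 31.
- 62% v 13%: 7.849 × (0.2356 + 0.2262) / 0.2401 = 15.10, so 16.
- 71% v 15%: 7.849 × (0.2059 + 0.2550) / 0.3136 = 11.54, so 12.

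The plan's arithmetic is right for this formula.

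**Step 2: the usual pooled chi-squared formula.** n1 = [1.96 √(3p̄q̄) + 0.8416 √(p1q1 + 2p2q2)]² / d², with p̄ = (2p1 + p2)/3. For 48% v 13%, p̄ = 0.3633, and (1.6328 + 0.5805)² / 0.1225 = 39.99. The other two scenarios give 21.33 and 16.39. Rounded up, the sizes are 40, 22 and 17.

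**Step 3: the planned test.** For each pair of group sizes, take every possible outcome, find those with one-sided Fisher p≤0.025, and sum their binomial probabilities under the assumed rates. The last column is the smallest exact 2:1 size that reaches 80%.

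| Scenario | Size in 9.1 (active/control) | Fisher power there | Fisher power at 40/20 | Size for 80% (power) |
|---|---|---|---|---|
| 48% v 13% | 31/16 | 60.1% | 73.5% | 46/23 (80.3%) |
| 62% v 13% | 16/8 | 46.6% | 95.5% | 28/14 (82.3%) |
| 71% v 15% | 12/6 | 46.7% | 98.6% | 22/11 (82.2%) |

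For 48% v 13%, 44/22 gives 77.2%. With 13% control responders, 40/20 reaches 80% once the active rate is 50.8%.

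**Step 4: is the choice of test what matters at 40/20?** An uncorrected pooled chi-squared test at 40/20 would have exact power of 82.1%, 97.9% and 99.5%, but its true one-sided size reaches 4.0%. Fisher's maximum size at 40/20 is about 1.3%. So 40/20 meets the target only under a test that is not planned and does not hold 2.5%.

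**Step 5: losses.** If fewer adherent subjects remain, Fisher power for 48% v 13% is 70.3% at 38/19 and 66.2% at 36/18. The other two scenarios stay at 93% or more. Reaching 60 analysed from 70-80 enrolled allows a loss of (70 − 60)/70 = 14% to (80 − 60)/80 = 25%. Reaching 69 (46/23) allows only (70 − 69)/70 = 1% to (80 − 69)/80 = 14%.

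**Step 6: interim looks.** Section 9.4 adds two looks at p<0.0013. Assuming Fisher's test at 20/10 and 30/15, the powers at 40/20 are unchanged to three decimals (0.735, 0.955, 0.986).

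**The case against.** Five points can be made for the plan.

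- *Fisher is not the only cause.* In the first scenario the step from 31 to 40 comes from using the unpooled rather than the pooled variance; only the step from 40 to 46 is Fisher's. This stands for the range. It does not rescue the chosen size: the pooled formula needs 39.99, so 40 had no margin even there, and what pushes it below 80% is Fisher.
- *The shortfall is small and confined to one scenario.* True: 73.5% against 80%, gone if the active rate is about 51% instead of 48%. That scenario also comes from two treatments per day, whereas this trial prescribes at most five per week, so its rates may not carry over. It is nevertheless the only one of the three that 9.1 describes with its own sham arm.
- *The low powers at 31/16, 16/8 and 12/6 are beside the point, because the trial plans 40/20.* Fair. They show that the 12-31 range is wrong for the planned test, not what power the trial has.
- *The plan's worked example, 60% v 25% with p = 0.01, shows that 40/20 is adequate.* It does not. That is the p-value for an observed result (24/40 v 5/20 gives 0.0105). If those were the true rates, Fisher power at 40/20 would be 64%.
- *The 70-80 enrolled provide slack, and nothing caps the analysis at 60.* Correct, but 9.1 and 5.2 assign that surplus to dropout, and 9.5 removes non-adherent subjects as well. It helps only if losses stay within the narrow limits shown above.

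Exact Fisher power is also saw-toothed (47/23 gives 79.8%), so 46/23 is the first 2:1 size to pass rather than a sharp threshold.

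**Conclusion.** The concern holds. The sizing in 9.1 and the test in 9.5 do not match, and the 12-31 range is wrong for the planned test; the correct range is 22-46. The planned 40 lies inside that range, so calling it conservative fails for 48% v 13%, where power is about 6.5 points below target. In the other two scenarios 40/20 is more than enough. These figures rest on the response rates in 9.1, an exact 2:1 split, and 40/20 being the adherent subjects analysed. Type I error is controlled and no bias arises. The consequence is a higher chance of missing a real effect if the true rates resemble the weakest cited study, together with a sample-size statement that conceals this. It should be fixed, but it does not threaten the validity of a positive result.

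**What to change.** In 9.1, replace the sentence giving the 12-31 range and the description of 40/20 as conservative with text such as:

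> Under the one-tailed Fisher's exact test (0.025), 80% power requires 46/23, 28/14 and 22/11 adherent subjects in the three scenarios, i.e. a treatment group of 22-46. With 40/20 adherent subjects, power is 73%, 96% and 99%.

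In 5.2, replace the statement that 40/20 is likely to be enough with the same three powers, and say that 40/20 counts adherent subjects analysed. This is wording only; the cost is a less favourable stated power.

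If the sponsor wants 80% in the first scenario, there are two options.

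1. **Aim for 46/23 adherent subjects.** This is 69 − 60 = 9 more analysed subjects. It fits within 70-80 enrolled only if losses stay at or below 1-14%.
2. **Specify Boschloo's exact test (one-sided 0.025)** before any unblinded look and subject to regulatory agreement. At exactly 40/20 its maximum size is 0.0249 and its power is 80%, 98% and 99%. There is almost no margin: for 48% v 13%, power is 79% at 38/19 and 76% at 36/18. This is more than wording. Section 9.6 records FDA input on outcome measures and sample size, the worked example in 9.5 would change, and the pad-weight and I-QoL secondary tests also use Fisher.

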### 1.4 Interventions and Duration

Study participants in the treatment group will receive surface electrical stimulation intended to treat incontinence. Participants in the control group will receive non-therapeutic surface electrical stimulation. Treatment is self-administered in an at-home environment according to a defined schedule. Outcomes are assessed after 12 weeks.

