#### 9.3 Blinding

Subjects will be blinded to their treatment group. As described in 6.6, with the exception of the firmware loaded on the Controller component, the devices used in the active and control groups are identical, so visualization and handling of the device by the subject will not compromise the blinding. The devices in both groups generate an electrical output that is perceived by the subject, which reduces the risk of subjects identifying themselves as in the control group. The device user manual (TR-1131-FORM-12) and subject instructions (TR-1131-FORM-15) have been modified/written to eliminate language that might suggest to a subject that she is one group or the other. Similarly, study personnel will be instructed to avoid use of language that might indicate which group a subject is enrolled.

Randomization as defined in 9.2 is implemented by an individual who does not interact with the subjects. Study staff who interact with the subjects are blinded to the randomization. Note however, that there is a risk that study staff who interact with the subjects may be informed of group assignment based on comments by the subjects during the study (e.g. if the subject

<sup>2 Richardson et al, "Pelvic floor electrical stimulation: A comparison of daily and every-other-day therapy for genuine stress incontinence", Adult Urology, 48(1):110-118, 1996.

describes the stimulation in a way that makes the stimulation identifiable). Such comments would be documented in the subject's Case Report File. This unblinding would have little impact on data integrity as the study personnel is not involved in the reporting of outcome measures.

Study personnel who analyze individual subject data will be blinded to group assignment. For example, baseline and 12th week episodes/day calculations and pad weight measurements will be made for each subject by blinded study personnel. Later, when group analysis is performed, blinding will be necessarily broken due to the unequal enrollment ratio.

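### Section 9.1 gives no power for the 40/20 design under the planned Fisher test: it is 73.5% at the plan's own 48% v 13%, and it falls at control rates above the 13-15% assumed

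*Combined protocol and SAP*

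**What the plan says.** Section 9.1 describes three calculations: "Each of these calculations target 80% power and assume an alpha of 2.5"%, with 2:1 allocation and a one-tailed test. The rates and resulting treatment-group sizes are:

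- 48% v 13%, both from one sham-controlled trial: 31.
- 62% from a second study, against the same 13%: 16.
- 71% from the sponsor's own ongoing study, against 15%: 12.

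The 15% is introduced with the words "Conservatively estimating the control responder rate at 15% (about the average rate reported in the AHRQ meta-analysis for the control groups in studies" that used vaginal EMS. The section concludes: "These three analyses suggest a treatment group in the range of 12-31 subjects". It then sets the target at 40 active and 20 control, and describes that choice as conservative. The one result shown for that size is "At that level of enrollment, responder rates of 60% and 25% would give p=0.01".

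Section 9.5 names a one-tailed Fisher's exact test at p≤0.025 as the primary analysis. It repeats the example as 24 of 40 active, while "5 of 20 (25%) from the control group responded". Section 5.2 relies on section 9.1 when it says that 40 and 20 subjects "is likely sufficient to achieve statistical significance with respect to the primary outcome measure".

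**The concern.** Three features of section 9.1 make the 40/20 design look better supported than the section shows.

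First, in a superiority comparison a cautious control rate lies above the value expected. An average is the expected value, so the word conservative does not fit the 15%. The other two calculations use a lower rate still, and nothing above 15% is examined.

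Second, the p-value of 0.01 stands where a power statement belongs. It says what would happen if exactly 24/40 and 5/20 were seen. It does not say how often the trial would succeed if 60% and 25% were the true rates.

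Third, the three sizes come from a normal-approximation formula, but the trial will be judged by Fisher's exact test, which rejects less often at these group sizes.

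The stake is interpretation. If the trial misses its endpoint, readers will weigh that result against the stated 80% target and the adequacy statement in section 5.2. If true power was well below 80%, they could take a miss as evidence of no effect when it is not.

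**Working it through.** **Inputs.** One-sided alpha 0.025, 80% power, 2:1 allocation, the three rate pairs and the 60% v 25% example come from section 9.1. The test and its threshold come from section 9.5. The group sizes, 40 and 20, come from sections 1.5, 5.2 and 9.1 and are taken as the numbers analysed.

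**Step 1: reproduce the plan's sizes.** The unpooled two-proportion formula at 2:1 is

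n(active) = (1.960 + 0.842)² × [p1(1−p1) + 2·p2(1−p2)] / (p1−p2)², with (1.960 + 0.842)² ≈ 7.849.

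- 48% v 13%: 7.849 × (0.2496 + 0.2262) / 0.1225 = 30.49, rounded up to 31.
- 62% v 13%: 7.849 × (0.2356 + 0.2262) / 0.2401 = 15.10, rounded up to 16.
- 71% v 15%: 7.849 × (0.2059 + 0.2550) / 0.3136 = 11.54, rounded up to 12.

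All three match. The pooled formula (40, 22, 17), the pooled formula with continuity correction (49, 28, 22) and the arcsine formula (38, 21, 17) do not.

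**Step 2: the same formula at a 25% control rate.**

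- 48%: 7.849 × (0.2496 + 0.3750) / 0.0529 = 92.67, so 93.
- 62%: 7.849 × (0.2356 + 0.3750) / 0.1369 = 35.01, so 36.
- 71%: 7.849 × (0.2059 + 0.3750) / 0.2116 = 21.55, so 22.
- 60%: 7.849 × (0.2400 + 0.3750) / 0.1225 = 39.40, so 40.

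Power at 40/20 by this formula is Φ[(p1−p2)/SE − 1.960], where SE² = p1(1−p1)/40 + p2(1−p2)/20. It gives 89% at 48% v 13%. At 25% control it gives 45%, 85% and 97% for 48%, 62% and 71% active, and 81% for 60% active.

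**Step 3: the worked example.** The one-tailed Fisher p-value for 24/40 v 5/20 is 0.0105, in agreement with the plan's 0.01.

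**Step 4: power under the planned test.** For each pair of true rates, sum Bin(a; 40, p1) × Bin(c; 20, p2) over all outcomes (a, c) with a one-tailed Fisher p-value of at most 0.025. Full enumeration gives:

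| Active rate | Control 13% | 15% | 20% | 25% |
|---|---|---|---|---|
| 48% | 73.5% | 66% | 47% | 31% |
| 62% | 96% | 93% | 83% | 70% |
| 71% | 99% | 99% | 95% | 89% |

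At 60% v 25% the power is 64%.

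**Step 5: separate the two causes.** At 48% v 13%, the fall from 89% to 73.5% is due to the test alone, since the rates are unchanged. The further fall from 73.5% to 31% is due to the control rate alone, since the test is unchanged.

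**The case against.** The strongest defence is that the trial does not enrol 12-31 treated subjects but 40, above the largest of its three calculations. By the plan's own formula, 40 covers every 25% pairing above except 48% v 25%, including the 60% v 25% example (40 needed, 81% power). A reader might infer that the trial needs 22-93 treated subjects instead of 12-31. The documents do not support that. The 25% appears only as an illustrative observed result, and five or more of 20 responders would occur with probability 0.17 even if the true rate were 15%. The range is a sensitivity range, not a corrected requirement.

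A second tempting inference is that this sham must produce a rate near 25%. Section 9.3 says "The devices in both groups generate an electrical output that is perceived by the subject", treatment is at home, the odds favour active treatment 2:1, and leaks are self-recorded. These features make a higher rate possible, but the documents give no figure, and the same influences would act on the active arm too. Chance variation in diary counts does not settle it. Simulating Poisson daily counts with no true change, a baseline of at least 7 episodes in 7 days, and the comparison of first and last five entries gives 27% responders at 1 episode a day, but 13% at 1.5, 9% at 2 and 4% at 3.

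Third, a reader might attribute all the control rates to vaginal stimulation. Only the 15% is so described. The electrode route behind the 13% is not stated.

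Finally, 15% is indeed higher than 13%, and choosing 40 over 31 is a margin. Both are fair. But that margin is measured by a formula more favourable than the planned test, and under that test 40/20 misses 80% at the plan's own first scenario. Section 9.6 records regulatory input on the sample size, which does not supply the missing power figures.

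**Conclusion.** The concern holds as a defect in the stated justification, not as proof that the trial is too small. Section 9.1 labels an average control rate conservative, examines nothing above 15%, and shows a p-value where power is needed. Under the planned test, 40/20 falls short of the 80% target at 48% v 13% (73.5%), and at 48% active it is below target at all four control rates examined. At 62% active it meets the target at control rates of 13%, 15% and 20% but not at 25% (70%). At 71% active it meets it at all four. At the plan's illustrative 60% v 25%, taken as true rates, power is 64%.

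The shortfall at 48% v 13% needs no assumption beyond the plan's own rates and test. The figures at 20% and 25% control are conditional on those rates, with the active rate held fixed. All assume 40 and 20 subjects analysed and a single final test at p≤0.025.

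**What to change.** In section 9.1:

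- Replace the 12-31 range as the basis for adequacy with the table of Fisher power at 40/20 above, naming the test and threshold of section 9.5.
- Beside the p=0.01 example, say that it is the p-value for 24/40 v 5/20, and that power at true rates of 60% and 25% is about 64%.
- Describe the 15% as an average from vaginal EMS control groups, not as conservative. Do not extend that description to the 13%.

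In section 5.2, qualify the adequacy statement by naming the rates at which 80% power is reached. Of those tabulated, these are 62% active with control rates of 13%, 15% or 20%, and 71% active with any control rate from 13% to 25%. State that 48% active does not reach 80% at any of them.

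The cost is a few sentences and one small table. No change in sample size, test or procedure is needed. The small downside is that the stated power becomes less favourable.
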